8.3. Exclusion Criteria

Subjects who meet any of the following criteria will not be enrolled in the study:

1. Received a prior IDH inhibitor.
2. Received systemic anticancer therapy or investigational agent <2 weeks prior to Day 1 (washout from prior immune based anticancer therapy is 4 weeks). In addition, the first dose of study treatment should not occur before a period ≥ 5 half-lives of the investigational agent has elapsed.
3. Received radiotherapy to metastatic sites of disease <2 weeks prior to Day 1.
4. Underwent hepatic radiation, chemoembolization, and radiofrequency ablation <4 weeks prior to Day 1.
5. Have known symptomatic brain metastases requiring steroids. Subjects with previously diagnosed brain metastases are eligible if they have completed their treatment and have

recovered from the acute effects of radiation therapy or surgery prior to study entry, have discontinued corticosteroid treatment for these metastases for at least 4 weeks and have radiographically stable disease for at least 3 months prior to study entry. Note: up to 10 mg per day of prednisone equivalent will be allowed.

6. Have a history of another primary cancer, with the exception of: a) curatively resected non-melanoma skin cancer; b) curatively treated cervical carcinoma in situ; or c) other primary solid or liquid tumor with no known active disease present that, in the opinion of the Investigator, will not affect subject outcome in the setting of current cholangiocarcinoma diagnosis.
7. Underwent major surgery within 4 weeks of Day 1 or have not recovered from post-surgery toxicities.
8. Are pregnant or breastfeeding.
9. Are taking known strong CYP3A4 inducers or sensitive CYP3A4 substrate medications with a narrow therapeutic window (Appendix 15.2), unless they can be transferred to other medications within ≥ 5 half-lives prior to dosing.
10. Exclusion criterion 10 removed in Protocol Amendment 4, Version 5.0.
11. Have an active infection requiring systemic anti-infective therapy or with an unexplained fever $>38.5^{\circ}\text{C}$ within 7 days of Day 1 (at the discretion of the Investigator, subjects with tumor fever may be enrolled).
12. Have any known hypersensitivity to any of the components of AG-120 or the matched placebo.
13. Have significant active cardiac disease within 6 months prior to the start of study treatment, including New York Heart Association (NYHA) Class III or IV congestive heart failure (Appendix 15.3); myocardial infarction; unstable angina; and/or stroke.
14. Have LVEF $<40\%$ by ECHO scan (or by other methods according to institutional practice) obtained within 28 days prior to the start of study treatment.
15. Have a heart-rate corrected QT interval (using Fridericia's formula) (QTcF) (Appendix 15.4) ≥ 450 msec or other factors that increase the risk of QT prolongation or arrhythmic events (eg, heart failure, hypokalemia, family history of long QT interval syndrome). Bundle branch block and prolonged QTcF interval are permitted with approval of the Medical Monitor.
16. Are taking medications that are known to prolong the QT interval (Appendix 15.5), unless they can be transferred to other medications within ≥ 5 half-lives prior to dosing or unless the medications can be properly monitored during the study. (If equivalent medication is not available, QTcF should be closely monitored.)
17. Have known active hepatitis B (HBV) or hepatitis C (HCV) infections, known positive human immunodeficiency virus (HIV) antibody results, or acquired immunodeficiency syndrome (AIDS) related illness. Subjects with a sustained viral response to HCV or immunity to prior HBV infection will be permitted. Subjects with chronic HBV that is adequately suppressed per institutional practice will be permitted.

18. Have any other acute or chronic medical or psychiatric condition, including recent (within 12 months of Day 1) or active suicidal ideation or behavior, or a laboratory abnormality that may increase the risk associated with study participation or investigational product administration or may interfere with the interpretation of study results and, in the judgment of the Investigator, would make the subject inappropriate for entry into this study.
19. Have known active inflammatory gastrointestinal disease, chronic diarrhea, previous gastric resection or lap band dysphagia, short-gut syndrome, gastroparesis, or other conditions that limit the ingestion or gastrointestinal absorption of drugs administered orally. Gastroesophageal reflux disease under medical treatment is allowed (assuming no drug interaction potential).
20. Have been committed to an institution by virtue of an order issued either by the judicial or administrative authorities.
21. Are dependent on the Sponsor, Investigator, or study site, per local institution regulations.
22. Have known medical history of progressive multifocal leukoencephalopathy (PML).

8.4. Subject Identification and Registration

Subjects who are candidates for enrollment into the study will be evaluated for eligibility by the Investigator to ensure that the inclusion and exclusion criteria (see Section 8.2 and Section 8.3, respectively) have been satisfied and that the subject is eligible for participation in this clinical study. The Medical Monitor will confirm eligibility for all subjects prior to randomization.

8.5. Subject Withdrawal Criteria

Subjects have the right to withdraw from the study at any time for any reason. A subject's discontinuation of study treatment or withdrawal from the study will not jeopardize the relationship with their healthcare providers or affect their future care. Subjects may choose to discontinue study treatment but agree to remain on study for follow-up contact. This decision must be recorded in writing by the study site.

Should a subject decide to withdraw, all efforts will be made to complete and report the protocol-defined study observations as completely as possible and to determine the reason for withdrawal.

In the event a subject discontinues study treatment or withdraws from the study, the Medical Monitor must be informed. If there is a medical reason for withdrawal, the subject will remain under the supervision of the Investigator until satisfactory health has returned.

When a subject discontinues study treatment or withdraws from the study, the primary reason for discontinuation or withdrawal must be recorded in the appropriate section of the electronic case report form (eCRF) and all efforts will be made to complete and report final study observations as thoroughly as possible.

8.5.1. Withdrawal from Study Treatment

Subjects may discontinue or be discontinued from study treatment at any time. In this situation, a subject without documented progressive disease by the Investigator should be followed for tumor

assessments until the development of progressive disease and/or survival. Subjects will be discontinued from study treatment for the following reasons:

- Withdrawal of consent
- Certain adverse events (as described in Section 9.8) including instances of Grade 4 QTcF prolongation
- A confirmed diagnosis of PML (Section 11.3.1) or Guillain-Barre syndrome (Section 11.3.2)
- Disease progression (subjects who are, in the opinion of the Investigator, benefitting from treatment [eg, slow progression] may be allowed to continue on study treatment with approval of the Medical Monitor)
- Death
- Investigator decision
- Subject decision to withdraw from treatment (subject may continue with PFS and/or survival follow-up)
- Protocol violation: non-adherence to study treatment regimen or protocol requirements
- Confirmed pregnancy (study therapy should be immediately interrupted based upon a positive urinary human chorionic gonadotropin [hCG] test, and permanently discontinued if confirmed by a serum β -hCG test)
- Lost to follow-up

All AEs should be followed until resolution or for a period of 28 days from the last dose of study treatment, whichever is shorter. If the subject withdrew from treatment because of an AE, every effort must be made to perform protocol-specified safety follow-up procedures.

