9.5. Blinding

The subjects, Investigators, the clinical research unit staff who deal directly with subjects, and the Sponsor will be blinded to study treatment assignment until documented disease progression. The IWRS will assign each subject specific Medication ID-labeled study drug containers. AG-120 and placebo will be packaged and labeled identically so that the study pharmacist will remain blinded to treatment assignment.

The subjects, clinical research unit staff, and Sponsor will remain blinded for the duration of the study unless emergency unblinding is required (see Section 9.6). Upon request by the Investigator, subjects and staff will be unblinded at the time of disease progression as confirmed by study sponsor.

An IDMC will review unblinded safety and other clinical data at scheduled meetings; the unblinded summaries will be prepared by an independent statistical center (Section 10.5.1).

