9.6. Unblinding

The need to unblind study treatment should first be discussed with the Sponsor's Medical Monitor (or Responsible Medical Officer), if at all possible. In the event of a medical emergency

or pregnancy in a female subject or in the sexual partner of a male subject, in which knowledge of the investigational product is critical to the subject's management, the study treatment may be unblinded for that subject by the treating Investigator. Investigators are encouraged to discuss a plan to break the blinding code with the Medical Monitor.

In case of an emergency, the Investigator may access the IWRS to reveal the identity of the treatment for that subject. Once the decision to unblind has been made, the Investigator must record the nature of the emergency that required the unblinding, along with the date and time of the unblinding on the proper source documentation and notify the Sponsor's Medical Monitor (or Responsible Medical Officer) of the unblinding.

In the event that a subject's treatment assignment is unblinded, either accidentally or in the case of emergency unblinding, the subject will be allowed to continue study treatment. In the case of emergency unblinding, if the subject is receiving placebo, cross over to AG-120 will not be permitted until documented progression.

Upon request by the Investigator, the subject and site staff will be unblinded to treatment assignment after documented disease progression (as assessed by the Investigator and after consultation with the Sponsor Medical Monitor), and subjects randomized to the placebo arm who still meet eligibility criteria will be given the opportunity to cross over to the active treatment arm and receive AG-120. For those subjects who cross over, placebo will not be counted as a prior line of therapy for the purpose of eligibility. If subjects cross over, they will follow the same assessment schedule as from C1D1. These subjects will continue to be evaluated for tumor response by the Investigator. If the treatment assignment is determined to be AG-120 upon radiographic disease progression, the Investigator may consider continuing AG-120, provided the subject appears to be clinically benefitting and there is no contraindication to continuing treatment beyond progression (see Section 9.8 for parameters for treating beyond progression).

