9.8.1.2. Continuation of Treatment Beyond Radiographic Progression

In the event of radiographic progression per RECIST v1.1 but in the absence of clinical deterioration, worsening ECOG performance status, or disease progression that may compromise organ function, the subject may continue to receive study treatment with AG-120 at the discretion of the treating physician in consultation with the Sponsor Medical Monitor. If there is clinical deterioration or continued radiographic progression documented on subsequent imaging, treatment will be discontinued and the subject will complete the EOT and Follow-up Visits, and enter survival follow-up.

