9.10. Duration of Subject Participation

9.10.1. Treatment Duration

Treatment with AG-120 or placebo will continue until disease progression, development of other unacceptable toxicity, confirmed pregnancy, death, withdrawal of consent, the subject is lost to follow-up, or the Sponsor unblinds or ends the study, whichever occurs first. Subjects who are determined to be on AG-120 upon study unblinding may continue on AG-120. For subjects who are determined to be on AG-120 upon radiographic disease progression and have demonstrated clinical benefit, PIs, with consult from the Sponsor, may keep the subjects on AG-120 after the disease progression. (See Section 9.6 for additional unblinding scenarios.)

Following discontinuation of study treatment, subjects are to attend a Follow-up Visit at least 28 days and no more than 33 days after the last dose for study assessments. When study treatment is withheld from a subject in order to resolve toxicity and the subject does not subsequently restart treatment, EOT is defined as the date when the study drug was first held.

Subjects should proceed with EOT assessments, safety, PFS, and survival follow-up. If the decision to not restart study treatment occurs outside of the 28-day safety follow-up window, the subject should proceed with PFS and survival follow-up.

Subjects will be contacted approximately every 12 weeks after EOT to assess survival status, HRQOL (until the start of new anticancer therapy), and to document receipt of subsequent anticancer therapy unless consent to participate is withdrawn.

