11. ADVERSE EVENTS

Monitoring of AEs will be conducted throughout the study (once subjects have received study drug); SAEs that are assessed as related to study treatment that occur >28 days post treatment also are to be reported. All AEs should be monitored until they are resolved or are clearly determined to be due to a subject's stable or chronic condition or intercurrent illness(es).

Adverse Event Reporting Period

Investigators will seek information on AEs at each subject contact, as outlined below. All AEs, whether reported by the subject or noted by study personnel, will be recorded in the subject's medical record and on the Adverse Event eCRF.

- After informed consent has been obtained but prior to initiation of study drug, only SAEs caused by a protocol-mandated intervention should be reported (eg, SAEs related to invasive study procedures such as biopsies).
- After initiation of study drug, all AEs and SAEs regardless of attribution will be collected at every visit until 28 days following the last administration of study treatment or until study discontinuation/termination or until initiation of subsequent anticancer therapy, whichever occurs first. Subjects will be assessed at the Follow-Up Visit to determine if any new AEs have occurred. After this period, Investigators should report only SAEs that are considered to be related to study treatment (AG-120/placebo).

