Upon request by the Investigator, the subject and site staff will be unblinded to treatment assignment after documented disease progression (as assessed by the Investigator and after consultation with the Sponsor Medical Monitor), and subjects randomized to the placebo arm who continue to meet eligibility criteria determined in the End of Treatment (EOT) visit will be given the opportunity to cross over to the active treatment arm and receive AG-120. For those subjects who cross over, placebo will not be counted as a prior line of therapy for the purpose of eligibility. If subjects cross over, they will start again with study procedures as at C1D1. These subjects will continue to be evaluated for tumor response by the Investigator.

An independent data monitoring committee (IDMC) will review the safety data on a regular basis to ensure the safety of treatment and proper conduct of the study. The first interim safety review meeting will be conducted when approximately 20 subjects have completed 2 cycles of therapy or have discontinued earlier; thereafter, meetings will be conducted every 3-6 months or on an ad hoc basis. No formal interim analysis for efficacy will be conducted before the primary analysis.

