8. EFFICACY ANALYSIS

For PFS, best overall response (BOR), ORR, DOR and other endpoints based on progression and/or response status, the primary analyses will be based on the independent central review by IRC. The endpoints based on Investigator assessment will be used as secondary analyses. Efficacy data after crossover will be analyzed separately.

After unblinding at local PD per Investigator assessment, subjects on AG-120 are allowed to stay on AG-120 if the treating Investigator deems they are clinically benefiting. The IRC will read all scans up to the discontinuation of AG-120. Subjects on placebo will no longer stay on placebo after radiographic disease progression and unblinding, hence no further scans will be read by IRC beyond the initial locally assessed disease progression imaging time point. Because of that, there is a potential systematic bias that subjects on the AG-120 arm could have PD called by IRC later than the locally assessed PD date; however, subjects on the placebo arm would systematically be censored by IRC analysis at the time of local PD if not concordant with local PD. To alleviate the potential imbalance between two arms, IRC assessments after the local PD from both arms will be excluded from the primary analysis of scan-related endpoints per IRC read. A sensitivity analysis by including all the scans read by IRC will be conducted.

All efficacy analyses will be based on the ITT set unless stated otherwise. If analyses are performed on more than one analysis set, the analyses on the ITT set will be considered primary. For each period, once the PD occurred, or the new anticancer therapy was initiated, all the subsequent tumor/response assessments will not be included in the tumor/response related summary analyses, but it will be included in the data listings.

Data after crossover (such as PFS) will be analyzed in a similar manner.

Listings for all efficacy endpoints will be provided.

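### Protocol 8.5.1 lets a subject with progression stay on study treatment, placebo included, while the protocol's other sections allow this only on AG-120

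*Protocol*

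**What the plan says.** Section 8.5.1 of the protocol lists the reasons for stopping study treatment. The entry for disease progression has a parenthetical exception: subjects who benefit in the Investigator's opinion, with slow progression as the example, "may be allowed to continue on study treatment with approval of the Medical Monitor".

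The term *study treatment* covers both products. Section 9.1, which describes it, lists AG-120 and matched placebo. Section 11 refers to "SAEs that are considered to be related to study treatment (AG-120/placebo", naming both.

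The other sections on treatment after progression are narrower:

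- Section 9.6: "If the treatment assignment is determined to be AG-120 upon radiographic disease progression, the Investigator may consider continuing AG-120". Section 7.1 has the same rule.
- Section 9.8.1.2: "the subject may continue to receive study treatment with AG-120 at the discretion of the treating physician", subject to clinical conditions.
- Section 9.10.1 ends treatment in either arm at progression and excepts only subjects "determined to be on AG-120 upon radiographic disease progression and have demonstrated clinical benefit". Section 9.7 is built the same way.

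On unblinding, Section 9.5 says: "Upon request by the Investigator, subjects and staff will be unblinded at the time of disease progression as confirmed by study sponsor". SAP Section 4 is also request-based: "Upon request by the Investigator, the subject and site staff will be unblinded to treatment assignment after documented disease progression". SAP Section 8 states: "Subjects on placebo will no longer stay on placebo after radiographic disease progression and unblinding".

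**The concern.** Section 8.5.1 is where a site looks for the stopping rules. It does not refer to Section 9.6 or 9.8.1.2, and the protocol states no order of precedence between sections. A site and Medical Monitor working from 8.5.1 could therefore keep a subject with progression on blinded placebo and be within the letter of the protocol.

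Two things are at stake for such a subject. Crossover to AG-120 depends on eligibility still being met at the end-of-treatment visit (Section 7.1), and eligibility includes ECOG performance status 0 or 1 (Section 8.2). While the subject stays on placebo that visit does not take place, and a subject who worsens in the meantime could lose the option. Palliative radiotherapy is barred during the blinded portion of the study (Section 9.6), so it too would wait.

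**Working it through.** No sample size, event count, power or alpha enters this point, so the check is a comparison of the texts.

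**Step 1. The rules side by side.**

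| Protocol section | Arm limit | Must the assignment be known? | Other conditions |
|---|---|---|---|
| 8.5.1 | None | No | Investigator's view of benefit; Medical Monitor approval |
| 7.1, 9.6 | AG-120 | Yes, it must have been determined | Clinical benefit; no contraindication; refers to Section 9.8 |
| 9.7, 9.10.1 | AG-120 | Yes, it must have been determined | Demonstrated benefit; Sponsor consulted |
| 9.8.1.2 | AG-120 | Not stated in this section | No clinical deterioration, ECOG worsening or threat to organ function; Medical Monitor consulted; stop on deterioration or further radiographic progression |

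Section 8.5.1 is the only row without an arm limit. It is also looser for AG-120 subjects, because it omits the 9.8.1.2 conditions and stopping rule.

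**Step 2. Does another rule close the gap?** Unblinding would do so if it were automatic. Sections 7.1, 9.5 and 9.6 and SAP Section 4 make it depend on an Investigator's request, and 8.5.1 does not prompt one. Medical Monitor approval is a real check. But Section 9.5 keeps the Sponsor blinded until documented progression, the Medical Monitor is the Sponsor's (Section 9.6), and 8.5.1 does not ask the approver to know the arm. A rule limited to AG-120 cannot be applied without that knowledge. Slow progression, the example in 8.5.1, does not identify the arm either, since it can reflect indolent disease on placebo.

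**Step 3. Is any analysis touched?**

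- Primary PFS by the independent radiology center: Protocol Section 12.13 counts progression when it first occurs, whether or not treatment continues. SAP Section 8 leaves central assessments after local progression out of the primary analysis in both arms. Continued placebo changes neither rule.
- PFS by Investigator: the event is the first progression, which has already occurred before 8.5.1 applies.
- OS: analysed by randomized arm with post-crossover data included (SAP Section 8.3), so no rule depends on 8.5.1.

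**Step 4. Length of a delay.** The documents do not give one. If the subject were reconsidered at the next scheduled scan (an assumption), the delay would be one scan interval: 6 weeks through week 48, and 8 weeks after that.

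**The case against.** The strongest reply is that the protocol, read as a whole, already settles the matter. Section 9.10.1 names placebo when it ends treatment at progression, and the same structure recurs in the Synopsis and in Sections 7.1 and 9.7. Sections 7.1 and 9.6 direct the reader to Section 9.8 for treatment beyond progression. On this view 8.5.1 is a loosely worded summary entry, not a competing rule. It also cannot act alone: a Medical Monitor would have to approve against text repeated across the protocol. The Investigator can request unblinding at any time after documented progression, which opens crossover for an eligible placebo subject and radiotherapy with approval.

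Much of this stands. The intended design is continuation on AG-120 only, so this is a wording fault and not a design choice, and several things must coincide before a subject is affected. The scenario also ends once all assignments are unblinded after the primary analysis. What the reply does not supply is a pointer from 8.5.1 to the stricter text, a precedence rule, or an approver who must know the arm.

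Two stronger readings should be set aside. A reader might infer that SAP Section 8 contradicts 8.5.1. Its sentence applies after progression *and* unblinding, so it shows intent but does not address a subject who stays blinded. A reader might also infer that unblinding never happens without a request. The documents are mixed: Section 7.1 describes blinding as lasting until documented progression, and SAP Section 8.8 says subjects will be unblinded at that point.

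**Conclusion.** The inconsistency is real and the sentence in 8.5.1 is wrong as written. Severity is low. The consequence is a possible delay to crossover, with some risk of losing eligibility, and to palliative radiotherapy, for a placebo subject whose Investigator sees benefit, does not request unblinding and obtains approval. That is probably rare; the documents give no figure. Crossover is delayed, not refused. No planned analysis is affected.

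A reader might try to put a survival cost on the delay from the planning medians for OS, 8 months on placebo and 12 on AG-120 (Section 12.2). The documents do not support that. Those medians run from randomization in whole arms, whereas the subjects here have already progressed and are typified in 8.5.1 by slow progression.

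The conclusion assumes that *study treatment* in 8.5.1 carries the meaning it has in Sections 9.1 and 11, and that a site could act on 8.5.1 without consulting the other sections.

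**What to change.** Replace the parenthetical in Section 8.5.1 with: *subjects who have been unblinded, are confirmed to be on AG-120, and meet the conditions of Section 9.8.1.2 may continue AG-120 with approval of the Medical Monitor*.

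This takes away nothing that the other sections allow. Amendments need IRB/IEC approval (Section 13.5), so the sentence should go into the next planned amendment; a stand-alone amendment across roughly 55 centers is not warranted. If no amendment takes effect before study-wide unblinding, the change will have little practical effect on the blinded-placebo case, though it would still bring 8.5.1 into line with the 9.8.1.2 conditions for AG-120 subjects. As an optional edit, the unblinding wording in SAP Section 8.8 could be aligned with the request-based wording in SAP Section 4. No analysis needs to change.
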